Furthermore, we assume that the the current source may have failed in a rail mode, with continuous 10 V output (instead of a 0.1 sec on duty cycle), the energy deposition might be considerably higher, $0.010 \text{ A/cm}^2 * 1 \text{ C/(A * s)} * (1500 * 2) \text{ seconds} = 30 \text{ C/cm}^2$ (or $300,000 \text{ C/m}^2$) at the source electrode.

Tissue damage has been detected at a minimum total charge of 216 C/cm² (2,160,000 C/m²) (Yuen, Agnew et al. 1981). Thus, even assuming the worst case circuit failure with the 10V power supply and an unconscious patient with an abraded scalp, the single fault charge density at the source electrode is never more than 0.14 (30/216) of the charge density that causes tissue damage.

A separate question is the likelihood of damage to brain tissue with the worst case circuit failure. In a study for epicranial tDCS stimulation in rats, (Liebetanz, Koch et al. 2009), Liebetanz and colleagues report that brain lesions were observed at a minimum cathodal electrode current density of 142.9 A/m² for durations greater than 10 min. For current densities between 142.9 and 285.7 A/m², lesion size increased linearly with charge density (current density × time); with an extrapolated zero lesion size intercept of 52400 C/m². If an EGI electrode were placed directly on the brain and a worst case electrical fault were to occur, the single fault charge density could exceed by a factor of 5.7 (300,000/52400) the zero lesion tissue safety limit at the source electrode, if it is allowed to exist for a full stimulation protocol.

However, the GTEN 100 electrodes are placed on the scalp (and face and neck). By careful modeling of head tissue conductivities (Gabriel, Peyman, & Grant, 2009; Turovets, Poolman, Salman, Malony, & [name], 2008) (**Figures 7 and 8**), we can determine that the current delivered at the scalp surface is attenuated by a factor of 100 or so at the brain. With an attenuation confidently estimated to range from 80 to 120, the total charge density of the proposed GTEN protocol to the brain would range from 0.07 (3750/52400) to .05 (2500/52400) of the lower bound of tissue damage of 52400 C/m².

Figure 7 shows the fall off in current level when 1 mA of current is applied to 6 source electrodes and 6 sink electrodes (Salman, Turovets, Malony, Eriksen, & [name], 2005). Note that in this simulation, although the average current density is 167 µA per each of the six electrodes, this simulation models the current injection as a point source (with the FDM and palette showing the diffused current in the nearby scalp), whereas the simulation in **Figure 8** provides finite element modeling of the current density at the electrode-skin boundary (illustrating the effect of the specific electrode surface area and conductivity pattern).

[figure not shown]

Figure 8. Finite element computations by [name] and [name] at the University of Utah with EGI's electromagnetic head model and realistic conductivity values for the skull. Here the scalp current density (at the perimeter of the 1 sq cm electrodes, right) is about 4 A/m² at the edges, and the maximum current density at the cortex is estimated as about 0.2 A/m², an attenuation factor of about 20.

Risk of Pain in Normal Operation

In normal operation, the circuit for current delivery is a constant current circuit. It is important to emphasize that the worst case calculations with the power supply voltage are therefore not relevant to the controlled current delivered in normal operation (we apologize if our previous presubmission material was unclear on this point).

In normal operation, the delivery of electric current through small (1 cm²) scalp electrodes causes itching and then pain as the current density is increased. This was a major motivation for the development of TMS, which uses the magnetic field of the electromagnetic coil to induce the

mirror image electrical current in the cranial space without electrical current flow through the scalp (which has extensive nerve endings). With the GTEN 100, we observe there are considerable individual differences in the pain that is experienced. As a result, we train the experimenter to encourage reports of itching or pain, and then to cease treatment with any reports of discomfort. Because there is no observed tissue damage at any of the levels used in our preclinical studies, and only minor reddening of the skin, the pain reflects the electrical stimulation of the scalp nerves rather than tissue damage.

Mitigating the Risk of Pain in Normal Operation

As mentioned above, estimations of safe and painless operation with conventional (large square sponges) tDCS (Bikson, Datta, & Elwassif, 2009) have suggested charge densities range from 343-960 C/m² (.0343-.0960 C/cm²). However, this calculation makes the common assumption in the tDCS literature that current is distributed evenly over the surface of the sponge. Instead, as would be consistent with classical physics model of the flow of current in a conductor, the current is distributed at the edge of the sponge, such that much higher current (and charge) densities have actually been delivered to the scalp at these perimeter locations in the conventional tDCS studies.

The same tendency for current to flow at the perimeter of the conductor is observed in simulations with the small (1 sq cm) electrodes of the GTEN 100 (Figure 8). However, the larger number of electrodes leads to greater perimeter distribution of the total current (Figure 8, right).

The first step to minimize the risk of pain is informing subjects that they can stop the procedure at any time just by letting us know they want to stop. This sensitivity to the patient's communications is an integral part of GTEN technician training. In addition, we tell each patient how, in case of emergency, they can take the chin strap and pull the Net off their head.

However, patients with epilepsy need an effective treatment, which may require brain current levels that are as close as possible to those induced by TMS. The present GTEN 100 protocol targets a current density at each electrode of 200 μ A/cm². We therefore minimize the risk of pain through iontophoretic (current induced) delivery of lidocaine that is mixed with the electrolyte. After a few minutes of iontophoretic application of lidocaine, our preliminary studies suggest 200 μ A/cm² is painless. If the subject detects any pain or discomfort, the current will be reduced so that the GTEN protocol (pulsed or sustained) is in fact painless.

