The GTEN 100 design has been modified to add a second Sentinel Circuit, in series with the first one, to assure that total current will be limited to 2 mA (and thus 2 A/m² as in the FDA "Q140561-S001 Comments to Sponsor". A triple fault (circuit fault and two Sentinel Circuit faults) is still possible, of course, but the risk is now very small.

Impedance Conditioning and Lidocaine Iontophoresis

In preparation for the neuromodulation session, an accessory for the the GTEN 100 is a new protocol for decreasing electrode-to-skin impedance (the Dermal Iontophoretic Bond or DIB protocol) by applying DC currents in order to draw ions from the electrolyte across the outer skin layer (stratum corneum) with iontophoresis. Scalp contact impedances are typically decreased from an initial ~ 100K Ohms to 20 to 40K Ohms after a few minutes of treatment.

This iontophoretic impedance conditioning protocol now allows the use of lidocaine with the gel electrolyte, such that the iontophoretic transfer results in topical anesthesia around the anode electrode sites, allowing higher current levels (200 μ A) to be applied painlessly. The iontophoretic current delivery includes cathodal (sink) electrodes adjacent to the anode

(lidocaine delivery) electrodes, so that there is minimal or no current delivery to the brain during iontophoretic delivery. Once the topical anesthesia is achieved, the anodal current can then be discontinued for those electrodes that will be cathodes (sinks) in the treatment protocol, while the topical anesthesia remains.

Computational Modeling of Head Tissues for Treatment Planning

The GTEN 100 includes an accessory software module, the GTEN Planning Module, that uses computational modeling of a finite difference model of electrical volume conduction through head tissues to target specific brain regions. The GTEN Planning Module includes the capacity for verification with bounded Electrical Impedance Tomography (bEIT), in which small (10 μ A) currents are injected at a specific frequency to test the planned GTEN targeting; if potentials measured at that frequency at multiple non-injecting electrodes are consistent with the model prediction, then the current flow through the head must also be consistent with the prediction, and the GTEN plan is acceptable.

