The GTEN 100 can be used with an atlas model of the head (similar age and sex as the patient). The atlas model has been validated for Electrical Source Imaging (ESI) in epilepsy diagnosis with EGI's FDA cleared GeoSource 2.0 software. In addition, the GTEN 100 can also be used with an individual electrical head model for the patient, which can be constructed from the patient's MRI (and the patient's CT or an atlas CT to characterize the skull bone density). The patient specific head model, and the warping of the atlas brain conductivity model to the patient's head shape (defined by photogrammetric localization of the 256 sensors and fiducial points) is constructed with the Modal Image Engine software and prepared for Electrical Source Imaging (ESI) with GeoSource 3.0 software. GeoSource 3.0 will be submitted for 510k clearance later in 2015 with GeoSource 2.0 as the predicate device and the Modal Image Engine as accessory software.

Intended Use

The intended use of the GTEN 100 is the application of electrical current to the brain for the purpose of manipulating the function and plasticity of the brain.

Indications for Use

The Geodesic Transcranial Electrical Neuromodulation 100 system is indicated to temporarily reduce the frequency of epileptic spikes in adults and adolescents over 12 years of age with partial onset seizures that continue to occur despite at least two trials of antiepileptic drugs at therapeutic levels.

Previous Submissions

Table 1 summarizes the EGI products relevant to both the Geodesic EEG System (GES) 400 and the GTEN 100.

The GES 400 was cleared under K131882 on February 12, 2014. The intended use of the GES 400 is:

The Geodesic EEG System 400 Series (GES 400) is intended to measure and record the electrical activity of the patient's brain. It can be used on adults, children, and infants.

Product Name	Clearance Status	Description; Any Changes for GTEN
GES 400	K131882	Hardware is identical except for current generation, which is upgraded from 100 μ A to 2 mA.
Net Station 5.0	Letter to file	The GTEN Interface Control allows selection of current source/sink electrodes and time course of current (DC, AC, pulse).
Geodesic Sensor Nets	K131882	No change.
Geodesic Photogrammetry System	K043309	No change.
Dermal Iontophoretic Bond	Not cleared; a component of the present product	Protocol for Direct Current delivery to decrease impedance of electrode-skin contact with iontophoresis, and to apply topical lidocaine.

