Figure 6. The GTEN Planning Module is designed to provide bEIT validation of the paths of the injected current through head tissues. **Left:** Illustration of the selection of three source electrodes (red) and 3 sink electrodes (blue). **Middle:** The forward projection of the electrical currents that are estimated to be impressed at the cortical surface. **Right:** The validity of the estimated current paths is tested through the bEIT computation, in which the EEG potentials at all non-injecting electrodes predicted by the finite difference model (FDM, green) is compared to the measured potentials created by the injected currents between channels 2 and 26 for Subject 12 (red). If the potentials created at the head surface are within 10% of the prediction by the electrical head model, then we consider the accuracy of the currents impressed on the cortical surface to be verified.

Figure 5. A simple illustration of Discriminative Cortical Surface vector targeting with two electrodes. From left to right: the red source (anode) is held constant and the blue sink (cathode) is moved from front to right to posterior right to posterior left. The cumulative charge delivered normal to each cortical patch is shown at each stage.

somewhat different non target regions receive current during each interval or pulse. Through computational optimization (in which the cost function is minimal non target current as well as maximal target current), the DCSV algorithm generates a set of source-sink electrode configurations that consistently deliver effective pulsed current flow to the target region but that create different (and thus minimized) current flow patterns in non-target regions over time (Figure 5).

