The resulting bEIT protocol is not the ill-posed imaging reconstruction of classical EIT, but a well-posed fitting of the conductivity to each tissue compartment (whose image or geometry is now easily obtained from MRI or an MRI atlas). When applied within the GTEN Planning Module, the bEIT validation (**Figure 6**) can be completed through impressing high frequency (200 Hz) low power (10 μ A) signals between the source and sink electrodes that were selected to optimize cortical targeting in the GTEN Planning Module. If the measured potentials (from the non-targeting electrodes, demodulated at the current delivery frequency) fit the prediction, then the delivered currents, the electrical head model, and the distribution of currents throughout the volume used in the GTEN Planning Module are verified as accurate.

Software Life Cycle and Risk Management

The GTEN 100 software, including the Net Station GTEN Control Interface and the GTEN Planning Module, have been developed under EGI's Quality System for a moderate level of concern. EGI's Quality System is audited internally on a regular basis, and it is audited externally by VDE. Design documents for the GTEN 100 include the Design Concept Report, Marketing Requirements Document, and Software Requirements Specification. Key functional components of the software have been designed and tested at the unit level, with regular regression testing and hazard reviews.

Risks of GTEN Treatment and Mitigation of Risks

The goal of GTEN treatment is to safely decrease the excitability of the cortex in order to suppress seizures. Whereas conventional tDCS (with large sponge electrodes) involves weak currents (and is well within limits for safety), it may not be as effective as rTMS, which induces larger currents in the brain. Furthermore, the higher current levels induced by rTMS are well within safety limits for tissue damage, and there is now fairly extensive evidence that slow rTMS (which we emulate with our protocol) has a very low risk of causing seizures. We therefore increased the GTEN current to 2 mA total, added lidocaine to increase comfort at this level.

We recognize the FDA's determination that, in epileptic patients, the GTEN 100 may present significant risk of worsening seizures or inducing cerebral discharges (possibly leading to kindling). We therefore request an Investigational Device Exemption. In addition, we detail the

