Once the GTEN Targeting is complete, the first treatment session is scheduled. At the beginning of that first session, the bounded Electrical Impedance Tomography (bEIT) procedure (**Figure 6**) is used with the selected sink-source electrode targeting configuration to test the prediction of the electric head model developed for that subject (with the individual's MRI or the atlas MRI and finite difference modeling). If the mean prediction of the recovered bEIT signal across recording electrodes is not within 10%, the model is judged to be flawed and the treatment is postponed until an accurate targeting model is created.

Once an accurate targeting model is achieved for the sink and source electrodes of the patient's GTEN Targeting of the presumed epileptogenic zone, it can be used for the subsequent treatment sessions, with the restriction that the placement of the Geodesic Sensor Net is replicated (within 2mm desired accuracy) in each session. Accurate placement is verified in each session with the Geodesic Photogrammetry System (**Figure 2**).

Iontophoretic Electrode-Skin Impedance Conditioning and Lidocaine Topical Anesthetic

Because scalp abrasion is prohibited, the electrode-to-skin impedance of the Geodesic Sensor Net typically begins at 50K to 100K Ohms. For consistent and effective delivery of electrical currents for neuromodulation, impedances of 20K Ohms are preferred. Furthermore, given the single current source of the GTEN 100, it is preferable to have all source (anodal) and sink (cathodal) electrodes at about the same impedance level (so that they divide the current evenly at about the 200 μ A per electrode target).

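### A scalp-potential match within 10% does not verify the current at the cortex, so the modelled dose carries an error that the plan does not quantify

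*Protocol*

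**What the plan says.** Protocol, Computational Modeling of Head Tissues for Treatment Planning: small test currents are injected, and if the potentials at non-injecting electrodes fit the model, "then the current flow through the head must also be consistent with the prediction, and the GTEN plan is acceptable".

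The Figure 6 legend supplies a tolerance for this check, namely 10% on the surface potentials. For a model that meets it, the legend concludes: "then we consider the accuracy of the currents impressed on the cortical surface to be verified". The section on validation of targeting with bEIT extends this to the whole head: "the distribution of currents throughout the volume used in the GTEN Planning Module are verified as accurate". It describes bEIT as "a well-posed fitting of the conductivity to each tissue compartment", with the geometry taken as known from an MRI or an atlas.

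The operating rule is in bEIT Validation of the Head Model: "If the mean prediction of the recovered bEIT signal across recording electrodes is not within 10%, the model is judged to be flawed". So in use the 10% applies to a mean across electrodes.

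The patient's own geometry is not required. The planning section states "The GTEN 100 can be used with an atlas model of the head", and even an individual model may take its skull density from an atlas CT.

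The model's output is then used in four places:
- as a covariate for efficacy (the section on targeting with the Geodesic Reciprocity Inverse Process, and The GTEN Planning Process);
- to predict seizure suppression from dose (Quantitating the Estimated Effective Dose) and for a dose-response analysis (Study Monitoring Committee);
- to review dose outside the target (Mitigating the Risk of Unwanted Plasticity);
- to estimate current in subcortical structures (Minimizing Effects on Nontarget Cortex).

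The protocol gives no bound on cortical-current error for a model that passes.

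**The concern.** The protocol states the inference as a necessity: if the scalp agrees, the interior must agree. The scalp, however, is a remote place from which to measure cortical current. By the protocol's own figures, scalp current density is attenuated by a factor of about 20 (Figure 8) to 120 (Mitigating the Risk of Tissue Damage with Electrical Fault) before it reaches the cortex. Several internal configurations can give nearly the same scalp potentials with different cortical currents.

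At stake is what the targeting analysis may conclude. The covariate is meant to test whether current oriented normal to the cortex matters. If the modelled dose can be off by a third in a patient whose model passed, a flat dose-response may reflect dose error and not a lack of effect. The non-target review has the same weakness.

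**Working it through.** **1. What can be reproduced.** The 10% is a criterion without a derivation, so there is no figure to recompute. Because the claim is one of necessity, a single passing model with a different cortical current refutes it.

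**2. Model and assumptions.** The protocol gives no conductivities or tissue thicknesses, so these are assumed:
- four concentric shells, outer radius 9.2 cm, scalp 5 mm, skull 5 mm, CSF 2 mm;
- conductivities 0.33 / 1.79 / 0.012 / 0.40 S/m (brain / CSF / skull / scalp);
- 256 electrodes of 1 cm².

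The series solution agrees with the analytic homogeneous sphere to better than 1e-14. At 2 mA, 10 electrodes against 10 give 0.20 A/m² at the cortex, against about 0.2 A/m² in Figure 8.

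**3. Quantity examined.** Ratio = cortical normal current in the passing model / cortical normal current in the reference model. The scalp error at electrode i is |V_i(model)/V_i(reference) - 1|. The operating rule is read as the mean of these errors being at most 0.10.

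**4. Wrong CSF thickness, conductivities refitted.** Brain, skull and scalp conductivity are refitted to the scalp potentials.

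| Montage | CSF 1 mm thinner: ratio (largest scalp error) | CSF 2 mm thicker: ratio (largest scalp error) |
|---|---|---|
| One pair | 1.30 (0.6%) | 0.64 (1.4%) |
| 10 v 10 opposite | 1.19 (0.5%) | 0.72 (1.6%) |
| 10 v ring | 1.24 (1.1%) | 0.67 (3.3%) |

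The mean scalp error is at most 0.3%. All six models pass easily, with cortical errors of +19 to +30% and -28 to -36%. A separately coded solution gave +18 to +31% and -27 to -36%. The figures move by a few points with electrode placement.

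**5. Wrong skull thickness, conductivities refitted.** With skull thickness wrong by a factor of 1.2 either way, the ratio stays within 0.98 to 1.025 in 36 cases. Skull thickness and conductivity trade off at scalp and cortex alike, so this is not the mechanism.

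**6. Conductivities not refitted.** Results depend on the assumed uncertainty and on how the 10% is applied.
- Mean rule, with skull conductivity uncertain by a factor of 2, brain and scalp 1.3, CSF 1.05 and skull thickness 1.2: 0.76 to 1.36. Requiring 10% at every electrode with usable signal gives about 0.83 to 1.19.
- Mean rule, geometry exact, extremes over wide conductivity ranges (brain 0.15-0.6, CSF 1.3-2.0, skull 0.003-0.04, scalp 0.2-0.7 S/m), electrodes above 5% of peak: 0.52 to 1.97 (pair), 0.56 to 1.60 (10 v 10).
- Strictest reading, same conductivity ranges, geometry exact and every electrode within 10% including those near zero: 0.88 to 1.21.

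**7. Effect on the dose-response analysis.** Let W be the predicted dose (the covariate) and X = W(1 + e) the true dose, with e of mean zero given W and standard deviation s. If Y = a + bX + noise, then E[Y | W] = a + bW, so the slope on W is b. This is Berkson-type error. With an assumed coefficient of variation c of 0.2-0.3 for predicted dose and s of 0.11-0.24, simulation returned a slope of 1.00 in all four combinations (true value 1). What falls is precision: the correlation of response with dose is multiplied by c / √(c² + s²(1 + c²)).
- Least favourable: 0.2 / √(0.04 + 0.0576 × 1.04) = 0.63.
- Most favourable: 0.3 / √(0.09 + 0.0121 × 1.09) = 0.93.

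**The case against.** **Limited role.** The protocol calls the dose an estimate and the targeting analysis post hoc and initial. The test for feasibility compares spike rates with baseline and does not use the covariate. Handling of covariate error can be left to an SAP. All of this stands and limits the severity. It does not rescue the statements that current is verified.

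**Refitting.** If bEIT refits conductivities per patient and the geometry is the patient's own, little error may remain. That is fair, and step 5 supports it for skull thickness. But the operating section describes a pass/fail test, does not make refitting explicit, and allows an atlas head.

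**Two stronger readings are tempting, and the documents support neither.**
- A reader might infer that dose error shrinks the dose-response slope, by 10-60% under the classical formula c²/(c² + s²). That formula applies when the measured value scatters around the truth. Here the covariate is the prediction and the truth scatters around it, so shrinkage is not shown. Fitted conductivities could add some classical error, but nothing at hand quantifies it.
- A reader might infer that the bEIT check produced the attenuation band ("With an attenuation confidently estimated to range from 80 to 120") and that the brain safety margin therefore fails. The band comes from head-tissue modelling. The section on tissue damage in normal operation cites bEIT studies alongside CT-based skull conductivity, then accepts that caution is warranted. The worst-case fault ratios reproduce: 300,000/80/52,400 = 0.07 and 300,000/120/52,400 = 0.05. At the regulator's attenuation of 30 the ratio is 0.19, and at Figure 8's 20 it is 0.29. The margin narrows but is not reversed.

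**Conclusion.** The point holds as a limited one. Agreement of scalp potentials within 10% shows only that the model is consistent with the scalp data. It does not bound cortical current to 10%, still less current throughout the head.

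In the assumed four-shell sphere, passing models differ at the cortex by roughly 20-35%, mainly when a geometric feature such as CSF thickness is not the patient's own. Without per-patient refitting, the mean rule also admits differences of tens of percent. These sizes rest on assumed conductivities, thicknesses and a spherical head. That the inference fails does not depend on the exact values.

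The modelled dose therefore enters the covariate, dose-response and non-target analyses with unquantified error. The consequence is lost precision and a null targeting result that cannot be interpreted. Neither a biased slope, nor an overturned safety margin, nor any effect on the primary spike comparison has been shown.

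**What to change.** - In the planning section, the Figure 6 legend, the section on validation of targeting and bEIT Validation of the Head Model, state that bEIT confirms consistency of scalp potentials only and does not bound cortical current to 10%.
- For each patient, report target, non-target and subcortical current as a sensitivity range over head models that meet the check, varying conductivities and CSF and skull thickness.
- Repeat the dose-response analysis across that range, and state in advance that a null result will not be read as evidence that oriented targeting is unimportant.
- Do not apply a classical measurement-error correction to the slope; with Berkson-type error it could inflate it.

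No change to dose or to any treatment rule is proposed. The cost is extra model runs and wider, less favourable dose figures.
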